Patients who are unable or unwilling to participate in any of the elements of prehabilitation will be excluded. These include those that have cognitive disability (including unconsciousness), cardiac or clinical instability, functional or anatomical impairment which impairs ability to participate, language barrier or patient refusal. Any language barrier will be identified by the primary clinical team and communicated to the research team. These patients will be excluded as we do not have the translating facility for the purposes of this study. Patients that have impending surgery within 72 hours of arrival to hospital will be excluded. Patients who are awaiting surgery in district hospitals or outside of Castle Hill Hospital will be excluded. A non-exhaustive list of exclusion criteria is included below.

Cardiac/ clinical instability such as:

- Recurrent unstable angina/ crescendo angina
- Untreated decompensated heart failure
- Malignant arrhythmias awaiting treatment
- Resting tachycardia (HR>100 bpm)
- Left ventricular outflow obstruction such as Aortic Stenosis with pre-syncopal or syncopal symptoms
- Unresolved acute pericarditis or myocarditis
- Second or third degree heart block without pacemaker
- Aortic Dissection
- Myxoma

Functional/ anatomical impairment such as:

- Severe musculoskeletal conditions that would prohibit exercise
- Amputees
- Registered blind

Patient recruitment and screening

Patients will be identified on admission via the acute admission board and during multi-disciplinary team (MDT) meeting. All acute patients waiting for cardiac surgery in CHH will be eligible to participate in the survey. As such, they will be approached, given information and invited to do so by a member of the research team.

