With regards to the pilot study, acute patients over 18 years old are first of all screened according to their route of admission (directly to CHH or via a DGH). Those that present directly to CHH and able to communicate in English will then be further screened with the above exclusion criteria. Whilst an interpreter can be organised for routine hospital care, this cannot be accommodated for the purposes of this pilot study. The language barrier may impede the participant from full participation. However, if this intervention was being implemented as routine practice or part of a bigger trial, the patient information leaflet, consent, questionnaires can be translated into the required language. In addition, a translator could be hired when the patient is undergoing the intervention. All eligible patients will be invited to participate in the project. They will be approached and provided information regarding the study. This will be explained in written and oral forms to each participant. Written consent is mandatory prior to any study related measures, intervention or questionnaire. Patients will also be asked if they would be happy to be contacted after the study to obtain feedback on the program as this guide future development.

Baseline data collection

The primary outcome will look into the acceptability of a multimodal acute inpatient prehabilitation program for patients and clinical staff. The study aims to identify barriers (if any) to organising, implementing and completing an inpatient prehabilitation program.

Secondary objectives are as follows:

1. Recording any physical changes to patient before prehabilitation, 7 days and 14 days after the intervention. If the surgery happens any other time before day 7 or 14, The measurements are repeated the day before the surgery. Measurements include
 - 6 minute walk test
 - Spirometry
 - Hand grip strength with dynamometer
2. Assessing quality of life and mental health before the prehabilitation, after prehabilitation but before surgery
 - EuroQoL (EQ-5D-5L)
 - Cardiac anxiety questionnaire (CAQ)
3. Identify any safety concerns related to prehabilitation program for this population, if any exist.
This will be identified by patient reported diary and notes entry from the staff.

Patients will be given a diary to document the duration of time they spent exercising, mood and any cardiac symptoms.

Information on post-operative complications and length of in hospital stay will also be collected.

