All study participants will be given a booklet containing psychoeducation information. The booklet aims to explain the emotions they may feel whilst being in hospital, symptoms of anxiety, suggest how to manage anxiety, behavioural strategies that may help and signposting if they require further support. In addition to this, the participants will be given access to audio on guided meditation and relaxation. Both the booklet and audio are designed with input from in-house clinical psychologist.

Patients will be asked to score themselves on CAQ and EQ-5D-5L on day 0 and on day 7 or day before surgery. During the second assessment of CAQ and EQ-5D-5L, patients will be asked if they have read or used either the psychoeducation booklet or audio. Hospital staff will be alerted of participants that score highly and considered high risk. In addition, they will be referred to the clinical psychologist or in-hospital psychiatry liaison team.

Additional information collection

All participants will be given a diary. They will be requested to record number of times they performed unsupervised exercise, and for how long. They are also asked to document their food intake. The diary is also used as a mood monitor. Participants are encouraged to write down how they felt, if they used the recommended technique and any benefit they may experience.

Participants will be interviewed for a feedback on the prehabilitation program. The questions will centre around their opinion of the intervention in terms of acceptability, enjoyment, usefulness, accessibility and achievability. We will be gauging their reception to the exercise, psychoeducation booklet as well as mindfulness audio.

Patient and public involvement

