New interventions and ideas are more likely to be successful when all stakeholders are involved in the planning as much as possible. Prior to designing our program, we interviewed inpatients awaiting cardiac surgery and those who had acute cardiac surgery to gauge their interest in prehabilitation. All the patients agreed with the concept of prehabilitation. Patients were keen to at least try and exercise whilst waiting for surgery. Patients were reporting that they have been told to avoid physical activity whilst awaiting surgery. We had mixed reaction to the proposed psychological intervention. Patients did not want any guidance on nutrition. They felt they knew what they needed and did not want nutritional information of their food displayed. Given this and the restrictions we have with time and budget, this element of prehabilitation is removed. All the patients interviewed admitted to a level of anxiety. This was mostly related to the waiting time for surgery, not receiving adequate information regarding the treatment plan and cancellations of surgery. Despite this, there was mixed reaction to our suggestion of providing psychoeducational information.

Based on the positive response from our sample group, we have designed our pilot inpatient prehabilitation program. Patient involvement will be an ongoing part in our project. We will be asking patients who will not be part of the intervention their opinion of the proposed program (investigations, assessments and interventions), the information provided to participants, potential barriers and how to overcome this. We will be consulting them on the materials and patient information sheet that will be provided to the participants. This will help guide us in further refining and improving the design of this study as well as future studies.

Safety

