We will be sending out questionnaires pertaining to the patient's mental health. Patient's that score highly or show any features of mental health problem that could impact their safety will either be asked to self refer for help or be contacted by a clinical psychologist. The intervention offered will depend on the severity of condition.

Outcome measures

The primary outcome is the feasibility and acceptability of the multimodal program. Feedback will be obtained from the patient regarding the acceptability, achievability and general interest in the program.

Feasibility will be assessed by determining the number of eligible patients, participants recruited, participated and retained at the end of the intervention, the proportion of intervention sessions delivered and fidelity of delivery. Moreover, participant recruitment, retention and adherence to the intervention will be measured, as well as any adverse events.

To determine the acceptability of the intervention and to explore barriers and enablers to the implementation of the intervention, interviews will be conducted amongst participants, and staff involved in referral and intervention delivery.

Secondary objectives:

- To identify a signal of efficacy for positive changes in physical health exercise, mental wellbeing, and quality of life (using tools described);
- To identify differences in length of hospital stay, complications and readmission rates to hospital following surgery compared to usual care (based on previously collected data);
- Indications of safety concerns with prehabilitation in acute inpatient population. This is based on reported adverse events

The 6 minute walk test, hand grip, quality of life measure, spirometry and cardiac anxiety score will be measured at three points, before the intervention, day 7 and day 14 or before the surgery. If the surgery happens before day 7, there will only be two measurements. Information on any cardiac symptoms and their association with the exercise will be documented.

The end of the trial is defined as the day of surgery for the last participant. Participants may choose to withdraw at any point of the trial. If they are changes in circumstances which would impact their ability to complete the trial, they will be withdrawn by the clinician.

Statistical method

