Data will be analysed at the end of the study. We will be analysing the data for the eligibility rate, recruitment rates, number of patient that participated and completed the intervention. We will be looking at the number supervised of sessions that were successfully delivered before the surgery as well as the number of unsupervised sessions that the participants achieved. Qualitative analysis will be used to determine the acceptability of the intervention and barriers to implementation.

Data of length of stay, complication rates and readmission rates will be collected and analysed. These can be compared to national data. Improvement in 6MWT, hand grip, EQ-5D-5L and CAQ will indicate potential efficacy of intervention.

Ethics

Ethical approval has been obtained from Hull York Medical School ethics committee. We have received REC approval via IRAS.

Data management

All staff handling patient data will need to comply with hospital data protection policy. The research team will need to have evidence of up-to-date Information Governance training. Data will be used according to the General Data Protection Regulation (GDPR) regulation. Only authorised research members will be given access to the required data. Electronic information on the study will be stored on approved devices provided by the institution. Written data obtained from the study will be kept in a locked cabinet in the department. All information collected will be anonymised. Individuals will not be identified through any reports or publications that result from the trial.

Discussion

Prehabilitation is one of the recommendations of Enhance Recovery After Surgery (ERAS). Although ERAS is well practiced in other surgical population (the society has been around since 2001), ERAS-C is relatively new (established 2017). Despite this, the implementation of prehabilitation in the UK has been slow. A recent survey found that only 13% of cardiac centres in the UK offered prehabilitation program to their patients compared to 66% for other surgical specialties.³¹ Only one centre offered multimodal prehabilitation as recommended by ERAS (nutrition, exercise, and psychological).³¹ The reluctance in adopting prehabilitation is likely to be multifactorial from financial, logistics, hesitance from clinician due to fear of precipitating an acute event, perceived limited waiting time and inconclusive evidence of improving outcome.

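### The acceptability and barrier interviews leave out eligible patients who decline, their reasons are not recorded, and refusal is listed as an exclusion, so acceptability may be overstated

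*Protocol*

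**What the plan says.** All references are to the Protocol.

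- **Outcome measures:** "The primary outcome is the feasibility and acceptability of the multimodal program". For acceptability, barriers and enablers, "interviews will be conducted amongst participants, and staff involved in referral and intervention delivery".
- **Baseline data collection:** "The primary outcome will look into the acceptability of a multimodal acute inpatient prehabilitation program for patients and clinical staff". The same section aims to find barriers to setting up, running and finishing the programme.
- **Additional information collection:** "Participants will be interviewed for a feedback on the prehabilitation program". No other patient group is named for this feedback.
- **Exclusion criteria:** "Patients who are unable or unwilling to participate in any of the elements of prehabilitation will be excluded". The examples include "functional or anatomical impairment which impairs ability to participate, language barrier or patient refusal".
- **Patient recruitment and screening:** patients are screened against the exclusions, and every eligible patient is then invited. Written consent must come before any study measure, intervention or questionnaire.
- **Primary objective, Outcome measures and Statistical method:** eligibility, recruitment, uptake, retention and completion are counted. Acceptability and barriers are analysed qualitatively.
- **Abstract, Setting, and Patient and public involvement:** a separate one-to-one survey asks inpatients who will not enter the pilot for their views on the programme, their interest and possible barriers.

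**The concern.** A patient who has agreed to take part has already passed the first test of acceptability. Asking only such patients makes the answer conditional on acceptance, and the likely direction of any bias favours the programme. The people best placed to explain why uptake is less than complete are those who were offered the pilot and said no. The plan counts how many joined but does not hold the decliners' own reasons.

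The counts are not secure either. Refusal can only happen after an invitation, and invitations go to patients already found eligible. Yet refusal sits in the list of exclusions. If a refuser is logged as excluded, the eligibility rate falls and the recruitment rate rises, and both belong to the primary objective.

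This is fixed at the design stage. No later analysis plan can recover reasons that were never collected. The Discussion presents the pilot as opening the way to larger studies, and their recruitment plans would rest on these rates and reasons.

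**Working it through.** The protocol gives no uptake or acceptability figure, so there is none to reproduce. The check compares who is asked with what is to be learned, then uses stated assumptions to show what the gap and the remedy amount to.

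**1. Who is asked**

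| Group | Counted? | Asked about acceptability or barriers? |
|---|---|---|
| Participants | Yes | Yes, by interview |
| Staff in referral or delivery | Not applicable | Yes, by interview |
| Inpatients outside the pilot who agree to the survey | Not part of the feasibility counts | Yes, but hypothetically and to refine the design |
| Eligible patients who decline the pilot | Only as eligible minus recruited, if not logged as excluded | No |

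**2. Can the overstatement be computed?** Let u be uptake, a acceptability among participants and b acceptability among decliners. Among all invited patients it is

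u × a + (1 − u) × b.

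None of the three is in the protocol. Assume a = 90% and u = 50%. With b = 0 the result is 0.5 × 0.90 = 45%. With b = 90% it is 90%. The gap therefore runs from 0 to 45 points according to b, which nobody measures. At u = 90% and b = 0 the result is 0.9 × 0.90 = 81%. This shows only that the size is undetermined. It does not estimate the bias, because the protocol plans a qualitative analysis and no acceptability percentage.

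**3. Denominator effect and yield of the remedy.** The sample size of 20 is from the Abstract. Uptake is assumed. Eligible patients invited = 20/u, rounded up, and decliners = invited − 20. The last column assumes that every decliner gives a reason. It is the chance that a barrier held by 20% of decliners is mentioned at least once, 1 − 0.8^k with k decliners.

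| Assumed uptake | Invited | Decliners k | Recruitment rate, refusers kept as eligible | Recruitment rate, all refusers logged as excluded | Chance barrier is mentioned |
|---|---|---|---|---|---|
| 30% | 67 | 47 | 20/67 = 30% | 20/20 = 100% | > 0.99 |
| 50% | 40 | 20 | 20/40 = 50% | 20/20 = 100% | 0.99 |
| 70% | 29 | 9 | 20/29 = 69% | 20/20 = 100% | 0.87 |
| 90% | 23 | 3 | 20/23 = 87% | 20/20 = 100% | 0.49 |

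As the plan stands, k = 0 at every uptake, because no decliner is asked. The 100% column is the extreme case. If only some refusers are logged as excluded, the rate lies between the two columns.

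**The case against.** The strongest reply is that the protocol does hear from patients outside the pilot. The survey is open to all acute inpatients waiting for cardiac surgery in the hospital and asks about interest, intensity and possible barriers. This stands in part: a reader might infer that barriers are asked only of people who said yes, and that would be wrong. But the survey asks what patients would think if they had the chance, serves to refine the design, is not tied to the primary outcome and is not aimed at those who refuse an actual offer.

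The stated barrier aim concerns setting up, running and finishing the programme. Participants and the staff who refer or deliver are natural informants for that, so it would go too far to say the aim cannot be met. Only the uptake part is weakened. Staff involved in referral may also report why patients said no, though second-hand.

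Two further inferences are tempting and not supported:

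- *That hesitant clinicians are a missing group.* The Discussion mentions "hesitance from clinician due to fear of precipitating an acute event", but as an explanation of slow adoption in the UK. The protocol describes no clinician veto, invites every eligible patient, and already interviews staff involved in referral, which plausibly includes the cardiology team.
- *That advice to rest is invisible to the plan.* Under Patient and public involvement, "Patients were reporting that they have been told to avoid physical activity whilst awaiting surgery". That came from patients the team interviewed, and both survey respondents and participants can report it again.

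**Conclusion.** The point holds in a limited form. The primary-outcome interviews omit eligible patients who decline, their reasons are not recorded, and listing refusal as an exclusion puts the eligible denominator at risk. Acceptability may be overstated. A reader might want to attach a number of percentage points to that, but every input would be invented, the outcome is qualitative, and the bias is zero if decliners hold the same views as participants.

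The denominator problem rests on the wording of the exclusion list. It arises only if refusers are in fact logged as excluded, which the text permits but does not require. For a 20-patient pilot this is a worthwhile correction that does not threaten the whole design: the feasibility counts do not come from participants alone, and the survey supplies some outside opinion.

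**What to change.** Amend Exclusion criteria, Patient recruitment and screening, and Outcome measures as follows.

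1. For each eligible patient who declines, invite an optional reason and enter it on the screening log as a code without identifiers. Before adopting this, confirm that it is compatible with the written-consent rule in Patient recruitment and screening, which covers study measures as well as questionnaires.
2. Remove refusal and unwillingness from the exclusions and count these patients as *eligible, not consented*, so that they stay in the denominator of the recruitment rate.
3. Report acceptability as *among participants*, beside the uptake rate and the tabulated reasons for declining.

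The cost is a field on the screening log, a check of the consent wording and a short table in the report. Wider staff interviews are not needed for this point and would add interviewing and analysis. The drawbacks are that some decliners will give no reason, that few reasons will be available if uptake is high, and that the recruitment rate may look lower.
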